#### Serotype at group level

Vaccine type (VT): If any of the serotypes covered in the 20-valent pneumococcal conjugate vaccine (PCV20), 13-valent pneumococcal conjugate vaccine (PCV13), the 7-valent pneumococcal conjugate vaccine (PCV7) or the 23-valent pneumococcal polysaccharide vaccine (PPV23) are detected either by UAD or culture.

PCV20: If any of the following serotypes 1, 3, 4, 5, 6A, 6B, 7F, 8, 9V, 10A, 11A, 12F, 14, 15B, 18C, 19A, 19F, 22F, 23F, and 33F are detected either by UAD or culture.

PCV13: If any of the following serotypes 1, 3, 4, 5, 6A, 6B, 7F, 9V, 14, 18C, 19A, 19F, and 23F are detected either by UAD or culture

cPCV7 (complimentary seven serotype): If any of the following serotypes 8, 10A, 11A, 12F, 15B, 22F, and 33F are detected by UAD or culture

PCV7: If any of the following serotypes 4, 6B, 9V, 14, 18C, 19F and 23F are detected by UAD or culture

PPV23: if any of the folling serotype 1, 2, 3, 4, 5, 6B, 7F, 8, 9N, 9V, 10A, 11A, 12F, 14, 15B, 17F, 18C, 19F, 19A, 20, 22F, 23F and 33F detected by UAD or culture.

DMB02-GSOP-RF02 5.0 Statistical Analysis Plan Template 05-Dec-2019
PFIZER CONFIDENTIAL
Page 30
TMF Doc ID: 98.03

Non-vaccine type (NVT): If none of the serotypes covered in PCV20, PCV13, PCV7, or PPV23 are detected from both UAD and culture.

Non-typeable (NT): A cultured isolate that could not be serotyped. This is a valid result and so will be summarized as a separate line. Note that this is not the same as a missing serotype result.

#### 6. ANALYSES AND SUMMARIES

One focus of this study is description and serotype distribution of *S. pneumoniae*, therefore statistical methods appropriate for these descriptive analyses will be used. Standard summary measures along with the number of participants used in the analysis will be displayed for all analyses. As a general rule, all proportions will be expressed as percentages.

#### 6.1. Primary Endpoints

## 6.1.1. Primary Endpoint 1 - Effectiveness of PCV13 among immunocompetent participants aged ≥60 years

VE is to be calculated as 1 minus odds ratio for PCV13 vaccination among cases and controls, multiplied by 100%, overall and restricted to immunocompetent participants.

## 6.1.1.1. Primary Endpoint 1- Main Analysis

## Pneumococcal Vaccination Status for Primary Endpoint

Pneumococcal vaccination status is defined as receipt of ≥1 dose of PCV13 or PPV23 and confirmed by electronic registries. Vaccination status will be categorized as: a) never exposed, b) ever exposed. Ever exposed will be subdivided into: i) exposed <5 years, and ii) exposed ≥5 and <10 years. Persons vaccinated ≥10 years will be considered unexposed.

The Madrid vaccination guidelines (Protocol Table 1) stipulate the timing of PCV13, and we will exclude following participants from the VE analyses:

- Immunocompetent participants who received PCV13 within one year after receiving PPV23
- Immunocompromising participants who received PCV13 within eight weeks after receiving PPV23
- Any participants who received PCV20

Note: Cases and controls include either radiologically confirmed CAP, not radiologically confirmed, or chest radiology not done. If more than 5% of the CAP cases are not radiologically confirmed, then a separate analysis will be performed selecting cases and controls only from the radiologically confirmed CAP cases.

The characteristics of cases and controls will be compared using the chi-square test.

DMB02-GSOP-RF02 5.0 Statistical Analysis Plan Template 05-Dec-2019
PFIZER CONFIDENTIAL
Page 31
TMF Doc ID: 98.03

For the primary endpoint, the cases will be the patients with CAP in whom PCV13 serotypes are identified by any method and the controls will be the patients with CAP without having VT serotype (even the CAPs for which the serotype was not identified). Multivariable logistic regression model (Appendix 3.3), will be applied to estimate odds of exposure to PCV13 among cases versus controls. All VE estimates will be calculated as  $(1 - \text{odds ratio}) \times 100\%$ . Both unadjusted and adjusted VE will be estimated. Patients' age, sex, study site and the variables deemed to be potential confounders on the basis of prior knowledge (e.g. nationality to be modeled as Spanish vs. non-Spanish; risk level to be modeled as low vs. at-risk vs. high-risk; BMI category to be modeled as obese vs. overweight vs. normal vs. underweight; PSI score as continuous; current drug abuse; antibiotic use within past 14 days; influenza vaccination within the last year; pneumonia in last year [ordinal variable, 0,1,2,3] and PPV23 receipt in past 5 years) will be included in the multivariable regression model for adjustment. Initially, we will employ bivariate models, and only the variables significant at p<.20 in the bivariate models will be included in the final model for adjustment.

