12.1.1. Defining Cases and Test-negative Controls

For the analysis of the primary endpoint, we will define cases as events involving hospitalised for CAP in whom PCV13 serotypes are identified by any method including UAD1 or routine culture of blood, pleural fluid, or other high-quality respiratory tract specimen. PCV13 VT serotypes are as follows: 1, 3, 4, 5, 6A, 6B, 7F, 9V, 14, 18C, 19A, 19F and 23F. Only sputum isolates from high-quality specimens (see Section 11.1) will be considered in assigning case status. All other episodes of CAP that met the inclusion criteria for the study, but for whom PCV13 or related serotypes are not identified from any source (ie, non-vaccine type [NVT] only) will serve as test-negative controls. Subjects with vaccine-related serotypes (eg, 6C) will be excluded from controls for the primary analysis. Subjects with VT serotype who also have an NVT or vaccine-related serotypes will be classified as cases. Subjects may only contribute one CAP event to any given VE analysis.

For PPV23 VE, cases will be those with one of 23 serotypes in PPV23: 1, 2, 3, 4, 5, 6B, 7F, 8, 9N, 9V, 10A, 11A, 12F, 14, 15B, 17F, 18C, 19A, 19F, 20, 22F, 23F, and 33F (including those where a NVT or vaccine-related serotype is also identified). Events with vaccine-related serotypes (either alone or in combination with an NVT) will be excluded from the controls for the primary analysis. Controls will be those with only nonvaccine serotypes (ie,

all other serotypes). Subjects with VT serotype who also have an NVT or vaccine-related serotypes will be classified as cases.

In sensitivity analyses, we will estimate PCV13 and PPV23 VE using different control group. In this case, controls will be defined as non-VT pneumococcal CAP (Broome method).¹³ That is, controls will be patients in whom pneumococcus is detected by blood/pleural/high-quality sputum culture, *BinaxNOW*[®], or UAD1/2 positive; but VT or vaccine-related serotypes are not identified from culture or UAD1/2. (ie, serotypes identified are not VT or related serotypes). In the second sensitivity analysis, we will define controls as CAP patients in whom pneumococcus was not detected by any method (culture, UAD, or *BinaxNOW*[®]), similar to a recently published TND.¹⁴

If PCV20 use is initiated in the surveillance area during the study, PCV20 vaccinated persons would be excluded from both case and control groups for the PCV13 VE analysis.

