%	12	15%	60%	9%	1:10	170	1692	1862	1960	50%	3920	3.4
enrolled	13	15%	60%	9%	1:10	170	1692	1862	1960	30%	6533	5.7

Table 6.Sample Size Scenarios for VE Calculations At Interim

- a. Base case values are highlighted in gray; 2.5% alpha was used for all scenarios and 80% power was used for all scenarios except #11. All calculations done with OpenEpi, Version 3, open-source calculator (Sample Size-Unmatched Case Control Study; available @ https://www.openepi.com/SampleSize/SSCC.htm) and used Fleiss method with continuity correction, which is consistent with estimates based on Fischer's exact test. For these calculations, 2.5% alpha was used to split alpha allocated between interim analysis and final analysis (ie, 2.5% to each analysis).
- b. Includes projected 5% of subjects with no valid pneumococcal serotype specimen result.
- c. Number of "CAP inpatients needed" is based on the percentage of CAP patients enrolled in prior column, which accounts for loss of potential subjects who declined participation or were not offered participation due to incomplete surveillance.
- d. Estimate 1800 CAP admissions annually in the surveillance area and 36% would be immunocompromised, leaving ~1150 immunocompetent CAP admissions annually and ~104 vaccine-type pneumococcal CAP cases.

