12.1.3.4. Serotype Distribution CAP Population (Secondary Analysis Population)

The Primary Analysis Population will include all events who:

- 1. Participant meets all inclusion and exclusion criteria.
- 2. Event has final diagnosis consistent with CAP.
- 3. Did not receive any pneumococcal vaccination ≤30 days prior to event urine sample collection.
- 4. Event with valid UAD1/2 test results or other pneumococcal serotype result (eg, from bacterial isolate).

Events with same serotype result involving rehospitalisation ≤ 30 days will be considered same event for this analysis.

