## Cases and Controls for VE against PCV13

The cases are the patients with CAP (i.e., enrolled population who have a final diagnosis consistent with CAP) and in whom PCV13 serotypes are identified by any method including UADs, routine culture of blood, pleural fluid, or other high-quality respiratory tract specimen. PCV13 serotypes are as follows: 1, 3, 4, 5, 6A, 6B, 7F, 9V, 14, 18C, 19A,

DMB02-GSOP-RF02 5.0 Statistical Analysis Plan Template 05-Dec-2019 PFIZER CONFIDENTIAL Page 9 TMF Doc ID: 98.03 19F and 23F. Only sputum isolates from high-quality specimens (Appendix 4) will be considered in assigning case status. Participants with VT serotype who also have a Non-Vaccine Type (NVT) serotype will also be classified as cases.

The following criteria must be met to be a control:

- hospitalized patient with CAP
- met the inclusion/exclusion criteria, and
- PCV13 or related serotype (e.g., 6C) are not identified from any sources

A second model will be developed excluding immunocompromised persons (Appendix 2.4) to evaluate PCV13 VE without those who may not be able to respond to the vaccine.

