#### Cases and controls for VE against PCV13

The cases are the patients with CAP in whom PCV13 serotypes are identified by any method including UADs, routine culture of blood, pleural fluid, or other high-quality respiratory tract specimen. PCV13 VTs are as follows: 1, 3, 4, 5, 6A, 6B, 7F, 9V, 14, 18C, 19A, 19F and 23F. Only sputum isolates from high-quality specimens (Appendix 4) will be considered in assigning case status. Participants with VT serotype who have also an NVT serotype will also be classified as cases.

The controls are the patients with CAP without a VT serotype (including the CAP events for which the pneumococcus was not identified or pneumococcus was present but the serotype was unknown) that met the inclusion and exclusion criteria. These will serve as test-negative controls. Participants with 6C serotype identified (VT serotype) will be excluded from the controls.

The definition of the immunocompromised persons is given in Appendix 2.4.

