#### 4.8.7. Sp- RAD+CAP Subpopulation

This subpopulation is composed of the participants in the RAD+CAP population who are not included in the Sp+ RAD+CAP subpopulation.

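### PCV13 controls need no valid serotype test, so patients whom the sample size counts as non-evaluable become controls by default

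*SAP*

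**What the plan says.** Protocol 12.1.1 takes as controls all other eligible CAP episodes, "but for whom PCV13 or related serotypes are not identified from any source (ie, non-vaccine type [NVT] only) will serve as test-negative controls". SAP 3.1 sets the same condition: "PCV13 or related serotype (e.g., 6C) are not identified from any sources". SAP 6.1.1.1 repeats it for the main analysis: "the controls will be the patients with CAP without having VT serotype (even the CAPs for which the serotype was not identified". SAP 3.3.1 goes further and names as controls CAP without a vaccine type, "including the CAP events for which the pneumococcus was not identified or pneumococcus was present but the serotype was unknown". Protocol 12.1.3.1 lists six criteria for the primary VE population. It refers back to 12.1.1 for case and control status and adds no requirement for a valid UAD or serotype result.

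Other text treats the same patients differently:

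- Protocol 9.1 describes controls as patients who test negative for PCV13 or related types, and says that participants are classified from their test results.
- Table 6 footnote b, on the enrolled column, reads "Includes projected 5% of subjects with no valid pneumococcal serotype specimen result". These patients lie outside the evaluable total.
- Protocol 12.1.3.4 admits to the serotype-distribution population only an "Event with valid UAD1/2 test results or other pneumococcal serotype result".
- SAP 4.8.1 builds a subpopulation with valid UAD results, but SAP 6.1.1.1 does not use it.

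**The concern.** A test-negative design compares patients who took the same test and differ in its result. Here the controls are whatever remains once cases are removed. Binax gives no serotype, so a patient whose UAD-1 is missing, insufficient, indeterminate or not done, and who has no serotyped isolate, can enter only one of the two groups. The same holds for a Binax- or culture-positive patient of unknown serotype who lacks a valid UAD-1, and that patient may well have a PCV13 type.

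Two things are at stake. Some true vaccine-type cases are counted as controls. Also, if PCV13 coverage among the untested differs from that of tested controls, the control odds of vaccination shift, and VE shifts with them. The plan also contradicts itself: its sample size discards patients whom its analysis definition keeps.

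**Working it through.** **Inputs.** Table 6 scenario 2 and SAP 2.2: control coverage 15%, VE 60% (OR 0.40), 9% vaccine-type, alpha 0.025, power 80%, 170 cases, 1,692 controls, 1,862 evaluable, 1,960 enrolled. Two-sided alpha comes from Protocol 12.4.1, and the Fleiss method with continuity correction from the Table 6 notes. Coverage among the untested is not given and is assumed.

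**1. Reproduce the plan's figures.** Case coverage is p1 = 0.4 × 0.15 / (0.85 + 0.4 × 0.15) = 0.0659. With p0 = 0.15, two-sided alpha 0.025, power 80%, ratio 1692/170 = 9.95 and continuity correction, the Fleiss formula gives 170 cases and 1,692 controls. Without the correction it gives 157 cases. Then 1,862 / 0.95 = 1,960, the enrolled figure. The 5% is therefore removed before the evaluable total is reached.

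**2. Apply the control definition as written.** Patients with no valid result: 0.05 × 1,960 = 98. They join the controls: 1,692 + 98 = 1,790, of whom 98 / 1,790 = 5.5% are untested. At the plan's case share, 98 × 170 / 1,862 = 8.9 of them would be unrecognised vaccine-type cases.

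**3. Effect on VE when missing results are unrelated to vaccination.** Control coverage = (1,692 × 0.15 + 8.9 × 0.0659 + 89.1 × 0.15) / 1,790 = 0.1496. VE = 1 - [0.0659/0.9341] / [0.1496/0.8504] = 59.9%, against a true 60%.

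**4. Effect when coverage c in the untested differs (assumption).** Control coverage = (1,692 × 0.15 + 98 × c) / 1,790, and VE = 1 - odds(0.0659)/odds(control coverage).

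| c | Control coverage | VE |
|---|---|---|
| 5% | 14.45% | 58.2% |
| 10% | 14.73% | 59.1% |
| 20% | 15.27% | 60.8% |
| 25% | 15.55% | 61.7% |
| 30% | 15.82% | 62.4% |

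The shift runs from -1.8 to +2.4 points. If 10% were untested, twice the plan's figure and also an assumption, unrelated missingness gives 59.7%, and c from 5% to 30% gives 56.3% to 64.6%.

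**5. Power.** By the normal approximation without continuity correction, power is 84.3% with 1,692 controls and 84.5% with 1,790. The extra controls add almost nothing.

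**The case against.** The best defence is that exclusion was intended and simply not written down. Protocol 9.1 has the central laboratory run Binax and both UAD assays on urine from every enrolled participant. Criterion 5 in 12.1.3.1 is timed to urine collection, and footnote b counts patients without a result as non-evaluable. The phrases about unidentified serotypes can be read as covering patients who had a valid UAD-1 that found no PCV13 type, and they are proper controls. Binax and UAD use the same urine, so a positive Binax without a valid UAD should be uncommon. This argument about intent is fair, and it is why the point is a contradiction to resolve rather than a settled decision to use untested controls. It does not cure the operative text, which a programmer would follow.

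SAP 5.3 does not settle it. It drops participants only from analyses that need the missing item, and VE status is set by any method. At most it can be read to remove patients with every test missing.

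The sensitivity analyses help only in part. Broome controls must have pneumococcus detected, so wholly untested patients cannot enter, but Binax-positive patients of unknown serotype can. The analysis with pneumococcus-negative controls (the Suzuki method) sets no valid-test condition either.

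Three stronger readings are tempting and are not supported:

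- **That VE is inflated to the mid-60s.** This needs 30% to 40% coverage in the untested, above every age-specific PCV13 value in Protocol Table 2 (highest 25.72%, September 2019), and for the larger values twice the projected missing share. It also uses a crude odds ratio, whereas Protocol 12.4.1 takes only adjusted estimates as final. Risk level, PSI score and site are candidate covariates, so adjustment should remove part of any bias that acts through them.
- **That renal failure with absent urine drives the bias.** Protocol Table 7 classes chronic renal failure as immunocompromised, so it lies outside the immunocompetent analysis that Table 6 sizes.
- **That untested patients generally become pneumococcus-negative.** SAP 3.4 exempts those with all three results missing. Only the residual wording of SAP 4.8.7, "participants in the RAD+CAP population who are not included in the Sp+ RAD+CAP subpopulation", fails to carry that exception, and no VE analysis in SAP 6.1 uses that set.

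**Conclusion.** The point holds as a gap in the primary control definition and a contradiction with Protocol 9.1 and Table 6 footnote b. Under the stated rule, patients with no valid UAD-1 and no serotyped isolate enter one side of the comparison only: about 98 of 1,960 in the base case. The likely effect is small. It is negligible if missing results are unrelated to vaccination, and about two points either way under the assumed coverage range at the projected 5%. The documents give no observed share of missing UAD results and no coverage for those patients, so neither a larger effect nor a direction can be claimed. Protocol section 3 warns that the PCV13-vaccinated are enriched for risk factors, so unrelated missingness should not be taken for granted. The reason to act is that the rule decides who is a control in the primary analysis and is cheap to state before status is derived alongside vaccination data.

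**What to change.** - In Protocol 12.1.1 and 12.1.3.1 and SAP 3.1, 3.3.1 and 6.1.1.1, state that a control must have a valid UAD-1 result and no PCV13 or related type found from any source.
- Exclude from the VE analysis participants with no valid UAD-1 and no PCV13-type isolate. For PPV23 VE, apply the same rule with UAD-1 and UAD-2.
- Define a valid UAD-1, including how a partly valid panel is handled. The SAP 4.8.1 set cannot serve as it stands, because one valid result among 24 serotypes is enough to enter it.
- Say whether a patient with a serotyped non-vaccine isolate but no UAD counts as a control. Footnote b would appear to treat that patient as evaluable.
- Report the number excluded, by vaccination status.
- Add two sensitivity analyses. One restricts both cases and controls to participants with a valid UAD-1, because the primary rule keeps culture-identified cases without UAD but drops such controls. The other uses the all-comers control group as now written.
- In SAP 4.8.7, carry over the SAP 3.4 exception for patients with all three results missing.

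The cost is some wording, one derivation flag and about 5% fewer controls, most of whom Table 6 already subtracts. No case is lost under the primary rule. The symmetric sensitivity analysis loses cases found by culture alone without a valid UAD-1.

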Adult vaccination with the 23-valent polysaccharide (PPV23) officially started in 2004, and with PCV13 in 2016 for some cohorts. Most adult pneumococcal vaccination occurs during annual influenza vaccination campaigns. Pneumococcal vaccination for adults in the Madrid region changed as of January 2018. An overview of pneumococcal adult vaccination is described in Table 1.

Note that for persons ≥ 60 years with past PPV23 administration, only those with underlying disease or at high risk will be given PCV13, and others without risk factors will not receive another pneumococcal vaccination (Table 1). Thus, in the ≥ 60 years age group, the population with PCV13 will be enriched for those with risk factors, and this will need to be accounted for in the analysis as a source of confounding (ie, confounding by indication).

Current PCV13 and PPV23 average uptake in Madrid Region as of March 2019 is described in Table 2, with a peak for PCV13 in people of 63 years old (see Table 2). People of over 60 years in the whole of Madrid region are 1,511,750 as of January 2018 (Instituto Nacional de Estadística, INE, www.ine.es).

The Regional Health System operates a database known as "Sistema de Información en Salud Pública y Alimentación" (SISPAL) [in English "Information System for Public Health and Food"] which includes information on previous vaccination history, including influenza, PPV23 and PCV13 vaccination, with lot number and date of administration per person.

Pneumococcal vaccination status will be based on whether receipt of ≥ 1 dose of PCV13 or PPV23 could be confirmed by electronic registries. All available vaccination data will be collected from the registry on subjects and time from vaccination will be incorporated in the analysis phase. Patients will be included regardless of the timing of their vaccination relative to their qualifying pneumonia admission but will be excluded from vaccine effectiveness

PFIZER CONFIDENTIAL CT45-GSOP-RF152.0 Low-Interventional Study Protocol Template 05-Dec-2019 Page 8 of 70

(VE) and serotype distribution analysis if they received pneumococcal vaccination \leq 30 days before hospitalisation for CAP because of risk of false positive UAD test. We will obtain previous influenza vaccination status (within the last year) via electronic registries as well.

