 - COVID-19 vaccination, dates and vaccines types.
 - RSV vaccination, dates and vaccine types.
- Hospitalisation data:
 - Dates and time of admission/discharge for qualifying admission.
 - ICU stay (yes/no).
 - Number of days in ICU.
 - Mechanical ventilatory support (invasive and non-invasive), if used and type.
 - Number of days of mechanical ventilator use.
 - Acute respiratory distress syndrome (ARDS) diagnosis during illness.

PFIZER CONFIDENTIAL CT45-GSOP-RF152.0 Low-Interventional Study Protocol Template 05-Dec-2019 Page 36 of 70

- Readmission within 14 days of discharge (If yes, dates of admission/discharge).
- Symptoms of qualifying pneumonia illness mentioned in inclusion criteria.
- Date of illness onset.
- Vital signs (initial respiratory rate, pulse oximetry, blood pressure, heart rate).
- Level of oxygen supplementation during pulse oximetry measurement (FiO2).
- SOC chest radiography results (eg, CXR and computed tomography [CT] scan), including if consistent with pneumonia per standard outlined in Section 11.3.
- SOC microbiology test results including test and specimen type:
 - Blood cultures.
 - Respiratory microbiology testing, including bacterial (eg, PCR and culture), viral testing (eg, RSV, influenza, and COVID-19), and Gram stain results.
 - All standard –of care COVID-19 testing during the qualifying illness will be recorded with result.
 - Pneumococcal testing (eg, *BinaxNOW*[®] or another pneumococcal antigen urine test).
 - Other body fluid/tissue sterile under normal conditions.
- CAP severity/prognosis scale (Confusion Respiratory Rate Blood Pressure [CRB-65] and Pneumonia Severity Index [PSI]) on presentation to hospital if information available from SOC testing to calculate score:
 - CRB-65 score [Contributing data elements: age, blood pressure, presence of confusion, and respiratory rate].
 - PSI score. Contributing data elements are:
 - Altered mental status.
 - Nursing home residency.
 - pH and partial pressure of arterial O2 (PaO2) from atrial blood or arterialised venous blood OR oxygen saturation level (SpO2) measured by pulse oximetry

PFIZER CONFIDENTIAL CT45-GSOP-RF152.0 Low-Interventional Study Protocol Template 05-Dec-2019 Page 37 of 70

and FiO2 during that assessment.

- Blood urea nitrogen.
- Serum sodium concentration.
- Plasma glucose concentration.
- Hematocrit.
- Presence of pleural effusion.
- Relevant medical history:
 - COPD.
 - Asthma.
 - Congestive Heart Failure.
 - Coronary Artery Disease (CAD).

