12.4.1. Vaccine Effectiveness

If either PCV13 or PPV23 coverage is <10% or >90%, we will assess whether valid VE estimates can be generated for the involved vaccine. If appropriate, we will proceed as follows; odds ratio of having received PCV13 and PPV23 for cases and controls with 95% CI for odds ratio will be calculated. See details on case and control assignment in Section 12.1.1. We will calculate VE as 1-OR x 100. In addition to constructing crude OR and VE estimates, we will perform unconditional logistic regression modelling to assess VE after adjustment for potentially confounding factors. Because of the risk-based approach to catch up vaccination in the over 60 cohort, we will also perform a second adjusted analysis, selecting non-vaccine-type controls similar the VT-serotype cases based on propensity score matching. Further, we will use a two-sided alpha of .025 for all analyses if final VE analysis is not conducted at the interim analysis. If interim analysis is final VE analysis, a two-sided alpha of .05 will be used in the final tables. A second model will be developed excluding immunocompromised persons to evaluate VE without those that may not be able to respond to the vaccine. Only adjusted estimates will be considered the final VE. Time from vaccination will be accounted for in the adjusted analyses. The comparison of the estimates of the effectiveness between PCV13 and PPV23 will be performed using the z-score test. The null hypothesis will be that there is no difference between the two estimates.

For the other study objectives, descriptive analysis will be carried out, presenting the absolute and relative frequencies of the qualitative variables and main measures of centralisation and dispersion in case of quantitative variables. Comparisons between proportions will be performed using χ^2 test, the Fisher's exact test, or the Likelihood Ratio test, as appropriate. For quantitative variables, the Student's t-test or the Analysis Of Variance (ANOVA) test will be used, and when data did not show normality in the Kolmogorov-Smirnov test, the Kruskal-Wallis and Mann-Whitney tests will be used.

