## Variables to be used to calculate the propensity scores

Variables for calculating the propensity score.

- Patients' age: continuous
- Sex: female=0, male=1
- Nationality: Spanish=0, non-Spanish=1
- Risk level: low-risk=0, at-risk=1, high-risk=2
- PSI score: continuous
- Antibiotic use within past 14 days: no=0, yes=1)
- Influenza vaccination within past one year: yes=0, no=1
- Pneumonia in the last year: ordinal value=0, 1,2,3
- Season of admission: Spring (Mar-May)=0, Summer (Jun-Aug)=1, Autumn (sep-Nov)=2, Winter (Dec-Feb)=3.
- PPV23 receipt in past 5 years: yes=0, no=1
- CAP event occurrence during COVID-19 pandemic: 0=not during COVID-19, 1=During COVID-19 (The study is started in the pandemic period; the variable will be used if we find a non-pandemic period during the study period)

The study site will be exactly matched. Note that the categorical variable will be put in the model like the ordinal values.

The conditional logistic regression will be employed to estimate odds of exposure to PCV13 among these matched cases and controls. The VE estimate will be calculated as  $(1 - \text{odds ratio}) \times 100\%$ . We will use a two-sided alpha of 0.05 for all analyses.

In the 2nd sensitivity analysis (PPV23 Naïve population), the cases will be the hospitalized CAP in whom PCV13 serotypes are identified by any method and had not received PPV23 in the last five years from the date of visit; the controls (also PPV23 Naïve population), will be selected using the propensity score matching as described above. A conditional logistic regression will be employed to estimate odds of exposure to PCV13 among cases versus controls in the PPV23 naïve population. The VE estimate will be calculated as (1 – odds ratio) × 100%. We will use a two-sided alpha of 0.05 for all analyses.

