#### Appendix 3.3. Calculation of odds ratio

To measure the effectiveness of the PCV13 and PPV23 against the target outcomes, the multivariable logistic regression model will be used Coefficient of the vaccine variable in the model will be exponentiated to estimate the odds ratio. To address the effect of the confounding

DMB02-GSOP-RF02 5.0 Statistical Analysis Plan Template 05-Dec-2019 PFIZER CONFIDENTIAL Page 55 TMF Doc ID: 98.03 variables, the variables that were independently associated with the outcome at p<0.10 in a bivariate analysis will be selected. When selecting the covariates for the final model, the rule of 10 events per covariate (Peduzzi et al 1996) will be followed. The vaccine effectiveness (VE) will be calculated as

VE = 1- adjusted odds ratio  $\times$  100.

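### SAP 6.1.1.1 and Appendix 3.3 give conflicting covariate rules for the primary VE model, so the adjusted VE is not uniquely specified and confounders the SAP names can be screened out

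*SAP*

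**What the plan says.** SAP 6.1.1.1 (Main Analysis) estimates PCV13 VE by multivariable logistic regression and refers to Appendix 3.3 for the model. It names age, sex and study site, together with "the variables deemed to be potential confounders on the basis of prior knowledge": nationality, risk level, BMI category, PSI score, current drug abuse, recent antibiotics, influenza vaccination, pneumonia in the last year, and PPV23 in the past 5 years. That makes 12 items. The prior-knowledge part is introduced as examples, so the list is not closed. One sentence puts these variables in the model without condition. The next says that "only the variables significant at p<.20 in the bivariate models will be included in the final model for adjustment".

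Appendix 3.3, which covers both the PCV13 and PPV23 models, says that "the variables that were independently associated with the outcome at p<0.10 in a bivariate analysis will be selected". It adds "the rule of 10 events per covariate", with no order of entry if cases run short.

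Protocol 12.4.1 asks for logistic regression adjusted for potential confounders, gives no p-value screen, and states: "Only adjusted estimates will be considered the final VE". The Protocol Summary notes that PCV13 recipients aged 60 and over will be enriched for risk factors and that "this will need to be accounted for in the analysis as a source of confounding". Because of risk-based vaccination, Protocol 12.4.1 also plans a second adjusted analysis by propensity-score matching. SAP 6.1.1.2 implements it as a sensitivity analysis.

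**The concern.** The SAP supports at least three covariate sets for one primary model: all named variables, those passing p<.20, and those passing p<0.10. For the p<.20 screen it does not say whether the bivariate test is against case status or vaccination. No variable is exempted from either screen.

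A confounder matters through its links with both vaccination and case status. A screen on crude association with case status looks at one link only. Where a risk factor raises both PCV13 uptake and the chance of being a case, vaccine protection partly masks its crude association, which makes it more likely to be dropped. That is the indication pattern the Protocol Summary describes.

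At stake is the definition of the primary estimate. SAP 5.1 applies no hypothesis test, so the adjusted VE and its interval are the primary result, and the choice among models could be made after seeing the data.

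**Working it through.** **1. Size on which the screens would run.** SAP 2.2 gives 170 cases and 1,692 controls (15% coverage in controls, VE 60%, 1:10, alpha 0.025, 80% power). Coverage in cases is 0.15×0.4/(0.85+0.15×0.4) = 0.0659. The Fleiss formula, two-sided, gives 157 cases without and 170 with continuity correction (1,700 controls at exactly 1:10), so the plan's figure is reproduced. These are immunocompetent cases (Protocol 12.5).

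Protocol Table 6 is an interim table, and SAP 7 drops the interim VE analysis, so a larger size is also relevant. Four-year accrual is 1,800×0.64×0.70×0.95×0.09×4 = 276 immunocompetent cases. Dividing by 0.64 gives overall sizes: 170/0.64 = 266 cases (1,692/0.64 = 2,644 controls) and, from the unrounded accrual, 431 cases. The control ratio is held fixed.

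**2. Chance that a screen drops a real factor.** The documents give no confounder effects, so odds ratios (ORs) and prevalences are assumptions. For a binary factor, SE(log OR) = √(sum of 1/cell), and the factor is dropped when |log OR|/SE is below 1.282 (p<.20) or 1.645 (p<0.10).

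Example: OR 1.3, 50% of controls, 170/1,692. The share in cases is 0.565, SE = 0.162, log(1.3)/0.162 = 1.62, and the drop probabilities are 37% and 51%.

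Three-level risk uses a 2-df Wald test with 36% high-risk (Protocol 12.1.2) and an assumed 10–30% low-risk.

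| Factor (assumed crude OR) | Cases | Dropped at p<.20 | Dropped at p<0.10 |
|---|---|---|---|
| Binary, 1.3, prevalence 30–70% | 170 | 37–44% | 51–59% |
| same | 276 | 22–30% | 34–44% |
| Binary, 1.5, prevalence 30–70% | 170 | 12–20% | 20–32% |
| same | 276 | 3–8% | 7–15% |
| Risk level, 1.3 at-risk and 1.6 high-risk | 266 | 10–28% | 18–42% |
| same | 431 | 2–13% | 5–22% |

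**3. What a drop does to VE (true VE 60%, assumed inputs).**
- One binary factor omitted, conditional OR 1.3 with case status: VE becomes 61.4–61.8% if its OR with vaccination is 0.5, and 58.2–58.7% if that OR is 2. In the second setting its crude OR is only 1.22–1.24, so the OR 1.3 drop rates above understate its risk of being dropped.
- Stronger link with vaccination (uptake 5–10% without the factor, 22–27% with it) and conditional OR 1.3–1.5: large-sample VE is 54–57%. A conditional OR of 1.3 then looks like 1.14–1.19 and is dropped 58–66% (p<.20) or 71–79% (p<0.10) of the time at 170 cases.
- Simulation with 12 independent normal covariates, 170/1,692, two strengths per sign pattern. Mean VE for full / p<.20 / p<0.10: effects of the same sign 61.3/59.3/58.3 and 60.4/56.0/53.7; alternating 60.1/59.5/59.3 and 60.0/58.4/58.1; opposite 58.5/59.3/60.1 and 58.2/59.6/61.2. Full minus p<0.10 therefore runs from −3.0 (58.2−61.2) to +6.7 (60.4−53.7) points. The mean absolute gap between the two cut-offs is 0.7–2.3 points.
- For scale, the crude 95% CI at 170/1,692 with OR 0.4 has SE = 0.316 and runs from 25.6% to 78.5%.

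**4. Does the whole named list fit?** The SAP rule counts covariates: 12 + PCV13 = 13, or 130 cases. Counting parameters (three sites 2, risk level 2, BMI 3, the other nine 1 each) gives 16, plus 1–2 for PCV13, or 17–18 overall. The immunocompetent model needs one fewer for risk level, so 16–17. That is about 160–180 cases. At 170 immunocompetent cases the list fits on the covariate count. On the parameter count it has almost no room: 10% missing leaves 153 cases, or 15 parameters. At 276, 10% missing leaves 248 and the list fits either way.

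**The case against.** The strongest reply is that confounding by indication is already handled. Protocol 12.4.1 answers risk-based vaccination with the matched analysis, which is itself an adjusted estimate. Its SAP list is fixed, has no p-value screen, and contains risk level, influenza vaccination and PPV23; for site, "The study site will be exactly matched". This stands. A reader might infer that the plan has no unscreened adjustment for indication, and the documents do not support that. However, the SAP ranks the matched analysis as a sensitivity analysis and its list lacks BMI and drug abuse. It neither settles the main model nor duplicates it.

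One could also say Appendix 3.3 is generic. It is not, because 6.1.1.1 cites it for this model. Reading age, sex and site as forced in is possible but unstated, and would still leave risk level, influenza vaccination and PPV23 exposed.

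It is also fair that 170 cases was the interim trigger and that drop rates fall with more cases. Both sizes are shown for that reason; SAP 2.2 still quotes 170.

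**Conclusion.** The conflict is real and rests on the text alone: the primary adjusted VE has no unique model, and either screen can remove confounders the SAP names. It should be fixed.

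The drop rates rest on assumed odds ratios and prevalences. Two tempting conclusions go too far. One is that the primary VE will be biased in a known direction: the illustrations move it both ways, and the documents give no confounder effects. The other is that the effect is negligible because the two cut-offs differ by only 0.7–2.3 points on average: the gap between the full model and the p<0.10 model reached 6.7 points in one setting. Direction and size are unknown, and none of these figures is an expected bias.

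Whether PSI belongs in the model is a separate question and is not part of this point.

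**What to change.** - Delete both p-value screens and state one rule, identically, in SAP 6.1.1.1 and Appendix 3.3.
- Replace the examples with a closed list, and include all named covariates in the primary model.
- State whether the 10-events rule counts covariates (13, or 130 cases) or parameters (about 16–18, or 160–180 cases).
- If complete cases are too few, keep age, sex, site, risk level, PPV23 in the past 5 years and influenza vaccination. Add the rest in an order written into the SAP before VE is analysed. On the parameter count this core needs 8 + 1–2 for PCV13 = 9–10 overall (90–100 cases), or 8–9 in the immunocompetent model (80–90 cases). It fits even the 117 cases of Table 6 scenario 1. Each added site costs one more parameter.

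The cost is SAP wording and code, with no new data. The downside is slightly less precision and some complete-case loss under SAP 5.3. Because SAP 7 plans no interim VE analysis and no coverage by case status, the rule can be fixed before any VE result is seen.
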